## 5.9.2 Laboratory

Microbiological analysis will be carried out on the lumen of all test valves. The presence of biofilm formation will be assessed and if present analysed by direct and indirect methods. Sections will be examined directly using episcopic differential interference contrast (EDIC) microscopy, which provides information on the development and structure of biofilms and shows interaction between the bacteria and catheter material. For indirect analysis, any attached bacteria and biofilm will be mechanically removed and re-suspended. This will then be analysed by culture (as described for urinalysis) and microscopy, using viability stains to quantify viable but non-culturable bacteria (VBNC).

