#### 4.2 Objectives

To assess preliminary safety, effectiveness, reliability, comfort and user acceptability of the valve with adults who have a long-term IDC and the feasibility of undertaking future community-based evaluation.

To do this we will:

- determine if the valve functions reliably i.e. automatically opens to drain urine within acceptable individual bladder volumes with a range of patients;
- determine if the valve functions effectively i.e. allows for the complete bladder emptying (< 100ml post void residual) during rest and daily activities;
- determine if the process of filling and automatic draining is comfortable and acceptable for participants;
- collect preliminary data on the potential for bioburden/biofilm following in human use of the valve;
- assess the feasibility of undertaking a future randomised control trial of the valve.

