## 5. CLINICAL INVESTIGATION DESIGN

This study a 'first in human' assessment of reliability, effectiveness, comfort and user acceptability with 16 long-term catheter users.

This study will be in one phase over 6 months, and compromise of 2 groups:

Group 1 (n=8)	Safety cohort (n=4)	Interim Safety review	(n=4)	
Group 2 (n=8)				(n=8)

Group 1- The valve will initially be tested in 8 participants who currently use a standard manual valve (without leg-bag). Such participants (and their bladders) will be accustomed to the filling and emptying of the bladder with an IDC in situ and therefore represent the most predictable and safest population on which to test the valve.

This first group will include a safety cohort of participants (n=4). All safety data will be reviewed from the initial 4 participants before further participants can undergo the study investigation. Review of the initial data will include an interim safety report submission to the Medicines and Healthcare products Regulatory Agency (MHRA) in line with the issued Notice of No Objection.

Once all relevant permissions to proceed have been granted, the valve will then be tested in the remainder of standard manual valve participants (n=4) to complete Group 1.

Group 2 - The valve will then be tested with participants (n=8) who currently use a drainage bag with free drainage in order to test the valve with people who are no longer accustomed to the process of filling and emptying the bladder (Group 2).

After use (in both groups), the valves will be examined microbiologically in the University of Southampton laboratory to detect bioburden and/or biofilm to ascertain a baseline for future studies.

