## 5.4 Recruitment and consent:

We will recruit 16 long-term IDC users (8 who currently use a standard manual valve e.g. a 'flip-flo' – with or without an attached drainage bag- and 8 who use just a drainage bag).

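### As worded, section 5.9.2 makes culture and viability counts conditional on biofilm being present, so the bioburden half of the promised laboratory baseline is not secured for biofilm-negative valves

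*Protocol*

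**What the plan says.** Section 4.2 lists, among the steps towards the study objective, to "collect preliminary data on the potential for bioburden/biofilm following in human use of the valve". Section 5 says that valves from both groups will be examined after use "to detect bioburden and/or biofilm to ascertain a baseline for future studies". Both places name bioburden alongside biofilm.

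Section 5.9.2 is the only place that says how this is measured. In order, it states:

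- Coverage: "Microbiological analysis will be carried out on the lumen of all test valves".
- Condition: "The presence of biofilm formation will be assessed and if present analysed by direct and indirect methods".
- Direct method: sections are examined by EDIC microscopy.
- Indirect method, recovery: "For indirect analysis, any attached bacteria and biofilm will be mechanically removed and re-suspended".
- Indirect method, readout: "This will then be analysed by culture (as described for urinalysis) and microscopy", with viability stains to quantify bacteria that are viable but cannot be cultured.

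The microbiology paragraph in section 5.6.2 says that used valves are collected, bagged individually and sent to the laboratory. It attaches no condition to this.

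**The concern.** Bioburden and biofilm are two different results, and the protocol asks for both. A valve may carry attached bacteria that do not amount to a biofilm. This matters here because a visit lasts at most 7 hours (section 5.1), so wear is short. If counting starts only once biofilm has been found, such a valve is never cultured.

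Two things are at stake. Bioburden results would come only from biofilm-positive valves, a subset chosen on a closely related finding. The remaining valves would have no bioburden result at all, which is different from a result of no growth. A later study using these data would need to know which of the two applies. The loss could not be repaired afterwards, because a valve not cultured when it is received cannot be counted later.

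**Working it through.** The protocol states no figure on this point, so there is nothing to reproduce. The check is mainly a comparison of texts.

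**1. What is wanted against what is conditional**

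| Result | Asked for in 4.2 and 5 | Given by 5.9.2 for a biofilm-positive valve | Given by 5.9.2, read literally, for a biofilm-negative valve |
|---|---|---|---|
| Biofilm present or absent | yes | yes | yes |
| Bacterial count (culture, viability stain) | yes, as bioburden | yes | no |

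**2. Do the neighbouring sentences remove the condition?** The coverage sentence says which valves enter microbiological analysis. It is satisfied if every valve is merely assessed for biofilm. The recovery sentence says what is taken off the lumen once the indirect method is used, and it includes attached bacteria as well as biofilm. It does not say when the indirect method is used. Only the sentence between them carries a trigger, and that trigger is the presence of biofilm. The section never says expressly whether a biofilm-negative valve is cultured, so two laboratories could both comply and return different data.

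**3. How presence is established.** On the literal reading the condition covers the direct method too, so EDIC microscopy would also wait for biofilm to be present. The section names no other means of establishing presence. This gap is a further reason to reword.

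**4. Number of valves.** Inputs: 16 participants (section 5.4), up to two visits each (section 5.1), and one to three valves fitted per visit (section 5.6.1, step 7; section 5.6.2, step 17). Section 5.6.2 bars anyone who stops on Day 1 from further testing, so one visit per participant is possible.

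- Fewest, all 16 tested: 16 × 1 day × 1 valve = 16.
- All complete both days, one valve each day: 16 × 2 × 1 = 32.
- Most: 16 × 2 × 3 = 96.

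The count would be below 16 if the trial stopped early under section 6.3.

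**5. Illustration only.** Let p be the share of valves with biofilm. The protocol gives no value, so the p used here are assumptions. Treating valves as independent, which is doubtful for valves from the same participant, the chance that no valve qualifies for a count on the literal reading is (1 − p)^n:

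| n valves | p = 0.01 | p = 0.05 | p = 0.10 | p = 0.25 |
|---|---|---|---|---|
| 16 | 85% | 44% | 19% | 1% |
| 32 | 73% | 19% | 3% | about 0% |
| 96 | 38% | 0.7% | about 0% | about 0% |

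For example, 0.95^32 = 0.194. Having no counts at all is a real possibility only if biofilm is rare. At any p below 1 the expected number of valves without a count is n × (1 − p). For n = 32 and p = 0.10 that is 32 × 0.90 = 28.8.

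**The case against.** The strongest reply is that 5.9.2, read as a whole with section 5, already means that every valve is analysed. It opens with all test valves, its indirect method recovers any attached bacteria, and section 5 sets out to detect bioburden in both groups. On this view the conditional clause means only that any biofilm found is characterised by both methods. The awkwardness noted in step 3 favours this softer reading. It is tenable, and it is why the point is one of ambiguous wording and not of a settled exclusion. It does not settle the matter, because no sentence says that biofilm-negative valves are cultured.

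A reader might infer something stronger: that bacteria are analysed only when biofilm is found, and that the baseline will be empty or drawn only from the worst valves. The document does not support that. Biofilm presence or absence would be known for every valve on either reading, so only the bioburden half is at risk. No mean count is planned, so an upward-biased mean would be the reader's own construct. Nothing says that uncultured valves would be reported as sterile.

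Two further replies carry weight. Bioburden is an exploratory objective, absent from the primary and secondary outcomes in section 4.3, and no stopping rule in section 6.3 depends on it. Section 7.1 also says that approved SOPs apply at laboratory sites, and a culture method could properly sit there. That softens the urinalysis point to an editorial one. It would also be too strong to say that no urine is collected: drainage bags collect it, section 9.3 lists urine assessments among CRF data, and the flow charts in Appendices B and C are not shown in the text available. What can be said is that no urinalysis method appears in that text.

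**Conclusion.** The point holds as a defect of wording with a practical consequence. Taken literally, 5.9.2 ties all culture and viability counts to the presence of biofilm, while sections 4.2 and 5 ask for bioburden too. A laboratory following that sentence would have a biofilm result for every valve and a bioburden result only for biofilm-positive ones.

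The size cannot be fixed from the protocol. It depends on an unstated biofilm prevalence and on a number of used valves between 16 and 96, assuming that all 16 participants are tested. The probabilities in the working show how the answer moves with assumed prevalence and are not estimates.

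The change is worth making because it secures half of a stated objective at little cost. It does not touch the primary or secondary outcomes or participant safety. If the sponsor already intends to culture every valve, the rewording only confirms it.

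**What to change.** Amend section 5.9.2 to state that:

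- removal, re-suspension, culture and viability staining are done on every used test valve, whether or not biofilm is found;
- biofilm presence or absence is reported separately for every valve, with the method that establishes it named;
- valves with no growth are reported as below the limit of detection and stay in the denominator.

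As a minor editorial correction, replace the cross-reference to urinalysis with the culture method or laboratory SOP actually used.

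The cost is some extra bench time, plates and stains. Used valves already go to the laboratory under section 5.6.2, so no visit procedure changes and participants bear no added burden.

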## 6. SAFETY REPORTING

The definitions of adverse events on which we have based our assessment below can be found in Appendix A. All safety events will be recorded using current UHS templates as per local procedure.

## 6.1 Adverse event (AE) recording & reporting:

For purposes of this protocol:

- All AEs will be recorded at participant visits or ad hoc phone calls with the participant and the research nurse and categorised as to expectedness, relatedness and severity.
- All non-solicited AEs will be reported. Depending on the nature of the event, the reporting procedures below should be followed. Any questions concerning adverse event reporting will be directed to the Chief Investigator in the first instance.
  - o Adverse Events form is sent to the Chief Investigator
  - Severity of AEs will be graded on a three-point scale (mild, moderate, and severe).
  - Relation (causality) and seriousness of the AE to the treatment will be assessed by the Chief Investigator.

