#### 5.1 Setting:

This 'first in human' phase will take place in controlled conditions at the Southampton NIHR Clinical Research Facility (CRF) at University Hospital Southampton NHS Foundation Trust.

Some of the key safety measures in place include:

- The Southampton NIHR Clinical Research Facility (CRF) is located within University Hospital NHS Foundation Trust, adjacent to the acute medical and intensive care wards.
- Clinical nursing staff based in the NIHR CRF are Immediate Life Support (ILS) trained (with annual updates) as a minimum.

- Clinical staff based in the CRF attend an emergency scenario training session at least annually.
- Standard Operating Procedures (SOPs) are in place for managing common medical emergencies such as anaphylaxis, syncope etc.
- Emergency resuscitation trolleys are in place throughout the facility.

Southampton

- Emergency call bells are tested every three months to ensure that they are in working order, and a bi-weekly check of pull cords is conducted to make sure they are accessible and have not been tied up or moved out of reach.
- As a hospital ward, the NIHR CRF has full use of the 24 hour emergency response teams in case of a medical emergency.
- A hospital style bed will be provided.

Each participant will attend two visits (up to a maximum of 7 hours per day) at the CRF testing the valve.

Appropriate refreshments will be provided, and travel expenses will be reimbursed.

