#### Testing Procedure

With the participant sitting (except when transferring to and lying on the bed for bladder scanning):

- 10. Participant puts on pad with pants to secure it in place
- 11. Record participant's self-reported bladder sensations
- 12. Scan bladder and record volume in Valve Log
- **13**. Participant fits the lowest pressure valve according to manufacturer's instructions for use and attach a drainage bag for urine collection.
- 14. Record Valve Batch/Serial Number in Valve Log.
- 15. Record participant's self-reported bladder sensations in valve log
- 16. Scan bladder and record volume in valve log
- 17. If the valve remains open with urine draining freely, replace with the next level pressure valve (up to 3 valves) until free drainage has ceased and the valve remains closed. Record Valve Batch/Serial Number in Valve Log.
- 18. Participant will be asked to stand, walk around and cough at specific intervals as per flowchart in appendix C.

URINARY CATHETER 'FILL AND FLUSH' VALVE:

SAFETY, EFFECTIVENESS, ACCEPTABILITY AND FEASIBILITY TRIAL Protocol Version 3.1 20/08/2019 - IRAS: 245818 - ERGO: 41448

- 19. Record participant's bladder sensations before each scan and:
  - a. If the volume is >400mls or the participant is experiencing discomfort
    - i. Ask the participant to contract abdominal muscles, press down on abdomen or bear down as if trying to pass urine to increase bladder pressure.
    - ii. If the valve opens, proceed as below (b).
    - iii. If the valve does not open, disconnect the valve, attach a new drainage bag and allow the bladder to drain. Stop the trial for that participant.
  - b. If the valve automatically opens:
    - i. Record the amount of urine voided
    - ii. Scan the bladder for any residual volume

As with Day 1, participants will be requested to drink a minimum of 500mls of fluids over the first two hours, then a minimum of 150mls per hour for the next 3 hours. They will be given a choice of drinks. After testing has ended for that day, participants will be given a new manual valve and/or drainage bag as per usual use.

If a participant has to stop testing during Day 1 they will not be eligible for any further testing. All data will be collected by an appropriately trained research nurse (RN).

**Valve Questionnaire**: After all testing is completed; participants will complete a Valve Questionnaire to assess the valve for comfort.

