#### 5.8 IDC Management after End of the study:

Once the participant has completed the study s/he will be advised to revert to his usual method of IDC management.

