#### 6.2 Serious Adverse event (SAE) recording & reporting

For purposes of this protocol:

- All SAEs will be recorded throughout the duration of the trial until two weeks after the participant completes the study.
- All non-solicited SAEs during study participation will be reported to the Chief Investigator within 24 hours of the research nurse learning of its occurrence using an Adverse Events form. In the case of incomplete information at the time of initial reporting, all appropriate information should be provided as follow-up as soon as this becomes available.
- Relationship of the SAE to study procedures will be assessed by the Chief Investigator, as should the expected or unexpected nature of the SAE.
- All non-solicited SAEs will be reported by the Chief investigator (or delegated member of the team) to the sponsor with 24 hours of becoming aware. All information is to be sent to [contact].
- Relevant ethics committees and regulatory bodies will also be notified as required.

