## 7.7 End of clinical investigation

The end of clinical investigation is defined as 2 weeks after the last participant's last visit (LPLV). This is in line with the safety reporting parameters for this study. The Investigators and/or the clinical investigation steering committee and/or the sponsor have the right at any time to terminate the clinical investigation for clinical or administrative reasons.

The end of the clinical investigation will be reported to the REC and Regulatory Authority within 90 days, or 15 days if the clinical investigation is terminated prematurely. The Investigators will inform participants of the premature clinical investigation closure and ensure that the appropriate follow up is arranged for all participants involved.

A summary report of the clinical investigation will be provided to the REC and Regulatory Authority within 1 year of the end of the clinical investigation.

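### Serious adverse events are to be recorded for two weeks after completion, but no scheduled contact falls in that window and the interim review is not timed to its close

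*Protocol*

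**What the plan says.** The window is set in Protocol section 6.2: "All SAEs will be recorded throughout the duration of the trial until two weeks after the participant completes the study". Section 7.7 places the end of the investigation two weeks after the last participant's last visit and gives the reason: "This is in line with the safety reporting parameters for this study". The two weeks are thus a deliberate safety period.

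On contacts, section 5.1 says "Each participant will attend two visits (up to a maximum of 7 hours per day) at the CRF testing the valve". The Day 2 procedures in section 5.6.2 close with a questionnaire: "After all testing is completed; participants will complete a Valve Questionnaire to assess the valve for comfort". Section 5.8 then adds only advice: "Once the participant has completed the study s/he will be advised to revert to his usual method of IDC management".

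On capture, section 6.1 says "All AEs will be recorded at participant visits or ad hoc phone calls with the participant and the research nurse". Section 6.2 names no further route, and its 24-hour reporting clock starts when the research nurse learns of the event.

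Two decisions use the safety data. Under section 6.3 the study is halted by one SAE that is at least possibly related, or by two severe or clinically significant adverse events (AEs) that are at least possibly related. Under section 5, "All safety data will be reviewed from the initial 4 participants before further participants can undergo the study investigation", with an interim report to the regulator.

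**The concern.** The protocol commits to a follow-up period but schedules nothing inside it. After the last visit an event enters the data only if an unscheduled call takes place, or if word reaches the team by some route that the protocol does not describe. In a first-in-human study of 16 people, an empty SAE listing for those two weeks could mean that nothing happened or that nobody asked.

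A halting rule can act only on events that reach the team. The clearance step after the first four participants has the same dependence. Because section 5 does not place the review relative to the two-week window, the review could be held while some of the four still have follow-up to run, and nothing in the text would show this as a departure from plan.

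**Working it through.** The protocol states no figure on this point, so there is none to reproduce. The check is a comparison of the window with the contact schedule, followed by a labelled illustration.

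**Step 1. Contacts against the window**

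| Item | Source | Inside the two weeks after completion? |
|---|---|---|
| Day 1 visit | 5.1, 5.6.1 | No, before it opens |
| Day 2 visit, ending with the questionnaire | 5.1, 5.6.2 | No, before it opens |
| Advice to return to usual catheter management | 5.8 | Not a follow-up contact |
| Ad hoc phone calls | 6.1 | Possible, but unscheduled |
| Follow-up arranged on premature closure | 7.7 | Applies only if the study closes early |

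Scheduled contacts per participant: 2. Scheduled contacts inside the window: 0.

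**Step 2. Who is affected**

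For a participant who returns, Day 2 begins with a fresh eligibility check and vital signs, so events after the Day 1 session get one scheduled look. Two periods do not: the two weeks after Day 2, and all follow-up of a participant stopped on Day 1, who under section 5.6.2 is not eligible for further testing.

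**Step 3. Timing of the interim review**

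Section 5 requires review of all safety data from the first four participants. Section 6.2 gives each of them a two-week SAE window. No sentence links the two.

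**Step 4. Illustration of what partial capture would cost**

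Assumptions, none of them in the documents: p is the risk per participant of an event after the last visit, and c is the share of such events that reach the team. Events during the supervised sessions are left out because staff would see them.

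Chance of recording at least one event in n participants: 1 − (1 − p·c)^n.

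- n = 16, p = 0.10, c = 1: 1 − 0.90^16 = 0.815
- n = 16, p = 0.10, c = 0.5: 1 − 0.95^16 = 0.560
- n = 4, p = 0.10, c = 1: 1 − 0.90^4 = 0.344
- n = 4, p = 0.10, c = 0.5: 1 − 0.95^4 = 0.185

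Over a range of assumptions:

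| c | n = 16, p = 10% | n = 16, p = 20% | n = 4, p = 10% | n = 4, p = 20% |
|---|---|---|---|---|
| 1 | 81.5% | 97.2% | 34.4% | 59.0% |
| 0.8 | 73.7% | 93.9% | 28.4% | 50.2% |
| 0.5 | 56.0% | 81.5% | 18.5% | 34.4% |
| 0.3 | 38.6% | 62.8% | 11.5% | 21.9% |

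If no event is recorded, the one-sided 95% upper limit on the true risk is (1 − 0.05^(1/n))/c. For n = 16 this is 17.1% at c = 1, 21.3% at c = 0.8, 34.1% at c = 0.5 and 56.9% at c = 0.3. For n = 4 it is 52.7% at c = 1 and 65.9% at c = 0.8. At c = 0.5 the formula exceeds 1, so four participants then set no limit at all.

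**The case against.** A reader might infer more than the text supports, in five ways.

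- *That the protocol contradicts itself, or that the follow-up does not happen.* It does not say so. A phone call is an allowed route, and an SAE reported by phone in the second week would be recorded as section 6.2 intends. The ascertainment is passive.
- *That events are caught only if the participant rings.* Section 6.1 does not say who starts an ad hoc call. The nurse may. The point is that no call is scheduled, so none is guaranteed.
- *That the interim review may clear the device early.* Section 5 is silent on timing. All safety data can be read to include the two-week data, and permissions to proceed are needed as well. Silence is not permission, but the reading is left open.
- *That section 6.1.2 foresees infections after the visits and leaves them uncollected.* That list concerns participants told to stop using the valve. It does not address the period after the visits.
- *That the percentages in the illustration measure this trial.* They do not. Both inputs are assumed, and the true SAE risk may be well below 10%.

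Other points on that side also have weight. Section 9.3 lists the medical file and GP correspondence as source documents, so an SAE could surface there, although no record check at two weeks is promised. The flow charts in Appendices B and C and the local safety templates are not shown. A two-week call is unlikely in charts titled for Day 1 and Day 2, but it cannot be excluded. Exposure is short and supervised, and the outcomes for valve opening, bladder emptying and comfort do not depend on what happens after the visits.

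What remains is narrow: the text at hand schedules no contact in a window that the protocol itself sets, and it does not tie the interim review to the close of that window.

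**Conclusion.** The point holds as a gap in assurance. The protocol sets a two-week SAE window and schedules no contact within it, so complete ascertainment is not assured after Day 2 or for participants stopped on Day 1. The halting rule and the review of the first four participants depend on these data, and the timing of that review is unstated.

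The firm result is the count: no scheduled contact inside the window for any of the 16 participants. How many events would be missed cannot be derived from the documents. The illustrative fall from 81% to 56% rests on an assumed 10% post-visit risk and 50% capture. The conclusion also assumes that the appendix flow charts and local procedures hold no two-week contact. The effectiveness and comfort results are unaffected. The change is worth making because it is cheap and lets an absence of recorded SAEs be read as one.

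**What to change.** In section 6.2, cross-referenced from 6.1, add one scheduled telephone call by the research nurse to every participant at the end of the two-week window, using a standard set of AE and SAE questions. Include participants stopped early, and state the date from which their two weeks are counted. Record the call, or the failed attempts, in the case report form so that missing follow-up is visible.

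In section 5, state that the interim safety review includes the completed two-week window for all four safety-cohort participants.

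The cost is sixteen short calls by existing staff and a pause of up to about two weeks before the interim review. The sample size, test procedures and end-of-investigation date do not change. If an unseen appendix or local procedure already schedules such a call, a cross-reference to it in section 6.2 would serve for the first part; the sentence in section 5 would still be needed.
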